## Objectives of the follow-up study:

To asses, in patients with psychogenic jerks, the long-term effect of treatment with BoNT on:

- improvement of motor characteristics and severity of the invalidating jerk of interest scored by a movement disorder specialist;
- improvement of motor characteristics and severity of the invalidating jerk of interest scored by the patient;
- the nature, distribution and severity of overall dyskinesia, scored by a movement disorder specialist;
- the frequency of the invalidating jerk of interest;

- whether patients consider treatment with BoNT effective, whether they judge that the benefits of treatment outweigh the side-effects and what they think about which treatment they have received (placebo or BoNT);
- disability;
- quality of life;
- · co-existent psychiatric disorders;
- the occurrence of adverse reactions;
- muscle weakness.

## 3. STUDY DESIGN

This project consists of two parts: a randomized placebo-controlled trial to assess the short-term effect of treatment of BoNT on psychogenic jerks and an uncontrolled follow-up study to assess the long-term effect.

# Study population

A total of 54 patients with one or more jerks of psychogenic origin will be included in the study. To be included, patients need to experience to be significantly impaired in daily functioning due to at least one specific jerk. For the trial phase of the study, patients will be randomized in a 1:1 ratio to treatment with BoNT or to treatment with placebo. After 16 weeks, when the trial phase of the study is over, all patients will be included in the study on the long-term effect of treatment. Patients with serious complications during the trial period will not be included in second part of the study. For our fMRI sub-study approximately 16 patients of our total study population will be included. They will be compared to 16 neurologically and psychiatrically healthy volunteers.

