#### Intervention

BoNT or placebo (0.9% sterile saline) will be injected in muscles involved in the jerky movement. In appearance the placebo is indistinguishable from BoNT. The muscles that will be injected will be determined by a neurophysiologist experienced in treatment with BoNT according to the pattern of movements visible and according to the involved muscles measured with EMG. The number of muscles injected may differ per patient. The neurophysiologist will determine the doses to be administered. These will be similar to those used for involvement of the same muscle by other movement disorders (typically dystonia). Placebo injections consist of an equivalent volume of 0.9% sterile saline. All injections will be given by an experienced neurophysiologist, who will remain blind to the treatment allocation and will not be involved in the outcome assessments.

As dose response differs individually, patients will be treated two times. The first treatment will take place after the baseline assessment. The second treatment will take place 3 months hereafter; this is the usual time interval in the treatment of dystonia. To optimize therapy, the dose and if necessary the injection sites may be adjusted in the second session according to degree of response and occurrence of muscle weakness. After 16 weeks, the trial period ends (see also time scheme, page 14).

[figure not shown]
After the trial period, all patients will be assigned to treatment with BoNT to establish the long-term effects. In this phase of the study, patients will receive a total of 4 times injections with BoNT at 3 month intervals. This results in a follow-up period of 12 months for all patients included in the study. The length of this follow up is considered necessary because of

several reasons. First and most important, an effect of therapy may diminish over time in these patients with a chronic disorder with frequently co-occurring disease. Second, it is considered an evaluation period for certain secondary study objectives, as it may take longer than the trial period before an effect on for example, concurrent psychiatric disease is observed. Finally, this way it is possible to evaluate whether optimalization of treatment results in better response to therapy in these patients.

Additionally in 16 of 54 patients an fMRI scan will be performed before and at the end of the trial (16 weeks).

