## 4.4 Sample size calculation

No prior results are available to clearly base the sample size calculation on. Hence, we chose to base our calculation on an expected difference in proportions reaching the primary endpoint between treatment with BoNT and placebo. For the expected proportions, we took the results of two prior trials studying the effect of BoNT into account. First, a trial in writer's cramp showed an effect in 32% of patients allocated to placebo and in 70% of patients allocated to BoNT on a patient rated primary endpoint. 11 Second, a cross-over trial in patients with motor tics showed no change in tics per minute in patients treated with placebo. Patients with tics and dystonia often have concurrent psychiatric disease as well. 12, 13 As the placebo effect may be large in patients with psychogenic disorders,  we expect that approximately one third of patients allocated to placebo treatment and approximately two thirds of patients allocated to BoNT may reach the primary endpoint. A two group Chi-square test with a 0,05 two-sided significance level will have 80% power to detect the difference between a control group proportion of 0,30 and a treatment group proportion of 0,70 (odds ratio of 5,4) when the sample size in each group is 24. As the side effects of therapy are mild and self-limiting and because only two injections are given in the trial period, we expect practically no withdrawals in this phase of the study. Assuming a withdrawal rate of 10 percent, we plan to include 27 patients per treatment arm, which means 54 patients in total.

This sample size calculation only concerns the trial part of this study, no power analysis was done for the follow-up study.

Regarding the fMRI study approximately 16 of the 54 patients participating in the BonT study will be included to take part in the fMRI study. Based on a study by Thirion et al., a minimum of 16 subjects is required for fMRI studies (see also amendment 2).

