# 7.4.1 Specific criteria for withdrawal

NA

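### Patients kept out of the follow-up after a serious trial-phase complication have no planned month-16 assessment, so the long-term results are conditional on having had none

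*Protocol*

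**What the plan says.** Under Study population, Protocol section 3 says that once the trial phase ends, "all patients will be included in the study on the long-term effect of treatment". The next sentence makes an exception: "Patients with serious complications during the trial period will not be included in second part of the study". Under Intervention, the same section returns to the general statement without the exception: "After the trial period, all patients will be assigned to treatment with BoNT to establish the long-term effects", and "This results in a follow-up period of 12 months for all patients included in the study". Section 5.1 also gives the four follow-up injections to all patients.

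Serious complications is not defined and is not tied to the serious adverse event definition in section 8.2.

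The follow-up objectives in section 2 include adverse reactions, muscle weakness and, for the patient's own view of treatment, "whether they judge that the benefits of treatment outweigh the side-effects". Section 7.1.2 compares month 16 with baseline and with week 16. Section 9.2 does this with paired tests, mentions mixed models for repeated measures, and states intention to treat for the trial results only.

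**The concern.** Stopping treatment and stopping assessment are two different decisions, and the exclusion sentence joins them. A patient with a serious complication leaves the second part altogether, and with it the month-16 video, interview, strength testing and questionnaires. The selection acts on harm, and harm is among the things the follow-up is meant to measure.

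Three features add to this.

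- The second part has no control group, so no comparison offsets the selection.
- The barred patients probably come more often from the BoNT arm. This is an inference: section 6.3 reports no side effects for saline in clinical studies, but the protocol gives no rate of serious complications by arm.
- The term is undefined, so entry to the second part is partly discretionary. Section 7.2 allows the code to be broken after a serious adverse event, so that discretion may be used with the allocation known.

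Section 10.4 raises the possibility that relief of the jerks uncovers psychiatric illness or leads to new somatic symptoms, and says its chance cannot be estimated. Section 3 justifies the 12 months partly because effects on psychiatric disease may take longer than the trial. If such a patient were admitted to hospital during the trial phase and this counted as a serious complication, the follow-up would lose a patient it was designed to observe.

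**Working it through.** **The plan's own figure.** The only computed figure is the trial-phase sample size in section 4.4: "A two group Chi-square test with a 0,05 two-sided significance level will have 80% power" with 24 per group, for 0.30 against 0.70. With pooled variance under the null hypothesis and no continuity correction:

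n = [1.960·√(2·0.5·0.5) + 0.842·√(0.3·0.7 + 0.7·0.3)]² / (0.7 − 0.3)² = (1.386 + 0.545)² / 0.16 = 23.3, rounded up to 24. Then 24 / 0.9 = 26.7, rounded up to 27 per arm, or 54 in total.

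The figure reproduces (power at 24 per arm is 81.2%). It does not bear on this point, because section 4.4 says that no power analysis was done for the follow-up.

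**Does any other section give barred patients a month-16 assessment?**

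- Section 7.3.4 lists the month-16 assessments. Section 3 (Assessments) places that visit in the follow-up study, which these patients do not enter.
- Section 7.6 gives patients who withdraw one last evaluation, or carries their last observation forward if they refuse. It does not mention patients barred from the second part.
- Section 8.2.3 follows the adverse event until it abates or is stable. It does not collect month-16 strength, disability, psychiatric status or the patient's judgement of treatment.
- The paired tests in section 9.2 need a month-16 value, so a patient without one drops out. A mixed model could keep that patient's baseline and week-16 values, but only by assuming that the missing month-16 value is predictable from them. It does nothing for adverse reactions or for the question about continuing treatment, which has no baseline value.

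None of these closes the gap.

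**How large could the selection be?** The documents give no rate of serious complications. Assumed rates of 1%, 2%, 5% and 10% of 54 patients would bar 0.54, 1.08, 2.7 and 5.4 patients.

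Suppose k of 54 are barred, all others are assessed at month 16, and a proportion p of those assessed respond. The rate in all 54 then lies between

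p(54 − k)/54 (no barred patient would have responded) and [p(54 − k) + k]/54 (all would have).

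With an assumed p of 0.60:

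| Barred (k) | Assessed | Lowest | Highest |
|---|---|---|---|
| 1 | 53 | 58.9% | 60.7% |
| 3 | 51 | 56.7% | 62.2% |
| 5 | 49 | 54.4% | 63.7% |

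The largest overstatement is p·k/54: 1.1 points for one patient, 3.3 for three and 5.6 for five. Whatever p is, it cannot exceed k/54, which is 9.3 points for five patients.

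**The case against.** The strongest reply is that the rule affects few people and that their safety data are not lost. Much of this stands.

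- Section 10.4 expects few serious adverse events, and section 4.4 expects practically no withdrawals in the trial phase.
- Trial-phase events are recorded (section 8.2), followed to resolution or stability (section 8.2.3), and counted at week 16, where adverse reactions are a secondary endpoint.
- Patients still in the study at week 16 are due the full assessment then.
- In section 3 (Study population) the exclusion follows the general statement directly and reads as a rule with its exception. Only the unqualified statements under Intervention and in section 5.1 are loose.

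Several stronger readings are tempting, but the protocol does not support them.

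- A reader might infer that the follow-up describes only patients who tolerated the first two sessions. Only serious complications exclude; patients with weakness, pain or flu-like symptoms continue. Because "patients will be randomized in a 1:1 ratio to treatment with BoNT or to treatment with placebo", about 27 of the 54 receive saline in those sessions, and their first BoNT exposure falls within the follow-up.
- A reader might see a conflict with the NA under section 7.4.1. That section concerns withdrawal of patients already in the study; the exclusion is a condition for entering the second part.
- A reader might say that no rule covers complications at other times. Section 7.4 lets the investigator withdraw a patient for urgent medical reasons at any point.
- A reader might set, say, 0 of 52 in follow-up against 2 of 54 over the whole study and call the first figure biased. The first is incidence in one period and the second is cumulative incidence. The 54 also includes about 27 patients who had no BoNT in the trial phase.

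It can also be said that month-16 data from patients off treatment answer a different question from the effect of continued BoNT. That is a reason to show them separately, not to leave them uncollected.

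**Conclusion.** The point holds in a limited form. The protocol removes patients with an undefined class of complication from assessment as well as from treatment, so the baseline-to-month-16 results are conditional on having had no such complication. The bias probably favours BoNT, on the inference that serious complications are more frequent under BoNT than under saline and that those affected would judge treatment less well.

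Its size is unknown. The range of about 1 to 6 points rests on an assumed 1 to 5 barred patients, an assumed 60% response and complete month-16 data in everyone else; the actual effect may well be near the lower end. The randomised comparison and the week-16 primary endpoint are untouched. This is an inexpensive improvement to the follow-up, not a threat to the trial's main result. Whether such patients should receive further injections is a clinical matter and is not judged here.

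**What to change.** Leave the decision on who is re-treated with the sponsor, and change the following.

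1. State that every randomised patient, including those barred from follow-up injections, is invited to the month-16 assessment. Show patients who are off treatment separately from those who continued.
2. Report long-term adverse reactions and weakness cumulatively from each patient's first BoNT injection. Trial-phase events in the BoNT arm then stay in both numerator and denominator, and patients first given saline enter at their first follow-up injection. A saline patient barred from the second part never receives BoNT and would be listed apart.
3. Reconcile the all-patients statements in section 3 (Study population and Intervention) and section 5.1 with the exclusion sentence, and say what counts as a serious complication for this purpose.

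The cost is a wording amendment and one visit of about 3 hours (section 7.3.3) per barred patient: 3 to 15 hours in total for 1 to 5 patients. The drawback is some off-treatment data in the long-term set, which separate presentation deals with. No sample size changes.

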#### Intervention

BoNT or placebo (0.9% sterile saline) will be injected in muscles involved in the jerky movement. In appearance the placebo is indistinguishable from BoNT. The muscles that will be injected will be determined by a neurophysiologist experienced in treatment with BoNT according to the pattern of movements visible and according to the involved muscles measured with EMG. The number of muscles injected may differ per patient. The neurophysiologist will determine the doses to be administered. These will be similar to those used for involvement of the same muscle by other movement disorders (typically dystonia). Placebo injections consist of an equivalent volume of 0.9% sterile saline. All injections will be given by an experienced neurophysiologist, who will remain blind to the treatment allocation and will not be involved in the outcome assessments.

As dose response differs individually, patients will be treated two times. The first treatment will take place after the baseline assessment. The second treatment will take place 3 months hereafter; this is the usual time interval in the treatment of dystonia. To optimize therapy, the dose and if necessary the injection sites may be adjusted in the second session according to degree of response and occurrence of muscle weakness. After 16 weeks, the trial period ends (see also time scheme, page 14).

[figure not shown]
After the trial period, all patients will be assigned to treatment with BoNT to establish the long-term effects. In this phase of the study, patients will receive a total of 4 times injections with BoNT at 3 month intervals. This results in a follow-up period of 12 months for all patients included in the study. The length of this follow up is considered necessary because of

several reasons. First and most important, an effect of therapy may diminish over time in these patients with a chronic disorder with frequently co-occurring disease. Second, it is considered an evaluation period for certain secondary study objectives, as it may take longer than the trial period before an effect on for example, concurrent psychiatric disease is observed. Finally, this way it is possible to evaluate whether optimalization of treatment results in better response to therapy in these patients.

Additionally in 16 of 54 patients an fMRI scan will be performed before and at the end of the trial (16 weeks).

## **Assessments**

Patients will be assessed at baseline, 16 weeks (the trial period) and after 16 months (follow-up study). Information on improvement, severity and frequency of jerks, the effect of therapy, disability and psychiatric disorders will be acquired with an interview and with questionnaires. Furthermore patients will be neurologically examined and recorded on video. A small part of the patients (n=16) will undergo an fMRI scan before and after treatment.

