## 5. TREATMENT OF SUBJECTS

## 5.1 Investigational product/treatment

Patients will be randomized to treatment with:

- 2 times injections with botulinum neurotoxin injections intramuscular with a 3 month interval or
- 2 times injections of placebo intramuscular with a 3 month interval.

Placebo will consist of 0.9% sterile saline. This is a frequently used placebo in studies on botulinum toxin. 

After the trial period, all patients will receive 4 injections of BoNT also with 3 month intervals.

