## 6.4 Summary of known and potential risks and benefits

Dysport® is contraindicated in individuals with known hypersensitivity to any components of Dysport®, careful consideration should be given before the injection of patients who have experienced a previous allergic reaction to a product containing botulinum toxin type A Side effects related to spread of toxin distant from the site of administration have been reported, which in some cases was associated with dysphagia, pneumonia and /or significant debility.. The occurrence of these side effects though are rare. Common side effects are: generalised weakness, fatigue, flu-like syndrome, pain / bruising at injection site. These side-effects are reversible and may be expected to resolve within two to four weeks.

No potential risk factors have been described concerning placebo(see SPC placebo).

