## 7. METHODS

## 7.1 Study parameters/endpoints

## 7.1.1 Main study parameter/endpoint

The primary study endpoint for the trial will be improvement of motor characteristics of the jerk of interest assessed with the Clinical Global Impression - Improvement scale (CGI-I). On this 7 point scale can be assessed how much the patients illness has improved or worsened relative to the baseline state. It can be rated as: 1, very much improved; 2, much improved; 3, minimally improved; 4, no change; 5, minimally worse; 6, much worse; or 7, very much worse. We will consider a score 1, 2 or 3 determined by an experienced researcher as reaching the primary outcome. The primary outcome will be determined 4 weeks after the second injection (t=16 weeks) as the optimal effect of BoNT is between 4 and 8 weeks after the injection. One researcher who is blind to allocated treatment will assess the CGI-I in all patients based on videos of the patient.

The CGI-I scale is one of the few rating scales that is considered suitable for psychogenic movement disorders at this moment.

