# 7.1.2 Secondary study parameters/endpoints

- 1. Clinical Global Impressions-Severity of Illness Scale (CGI-S) for motor severity of illness, including other jerks, rated by the investigator;
- 2. Severity and improvement of the jerk of interest according to the patient. The CGI-I will be used for the improvement of the jerk of interest, including other jerks, rated by the patient; The severity will be measured using the CGI-S and the Visual Analogue Scale(VAS). This is a self assessment scale drawn by the patient on a 10 cm line, on which 0 indicates no disease burden and 10 indicates the worst possible disease burden: 
- 3. Severity of general dyskinesia and myoclonus according to a movement disorder specialist using two scales; the unified myoclonus rating scale (UMRS) , which measures the nature, distribution and severity of dyskinesia and a recently developed PMD scale, which quantifies the impact of the movements and is a valid measure of severity. It is used to assess PMDs and test the efficacy of intervention strategies;
- 4. Frequency of the jerk of interest during the psychiatric interview;
- 5. The patients answer to the following questions: considering all advantages and disadvantages of this treatment, is the improvement such that you want to continue this treatment or not? 

- 6. AMC Linear Disability Score (ALDS), a generic instrument which includes ADL and instrumental activities of daily living;
- 7. Short-Form-36(SF-36), a generic Quality of Life scale, suitable for measuring disease burden and health benefits produced by a wide range of different treatments;
- 8. Psychiatric evaluations including the Mini-International-Neuropsychiatric Interview Plus (MINI-Plus) and several questionnaires concerning symptoms of depression, anxiety and obsessive-compulsive disorders. The Yale Tic severity scale and the Premonitory Urge for Tics Scale (PUTS), will be used for assessment of tics and evaluation of premonitory urge in the jerk of interest;
- 9. Evaluation of adverse effects via interview and neurological examination;
- MRC scale for testing muscle strength and sensibility;
- 11. Changes in brain function assessed with fMRI.

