## T= 16 weeks:

- Neurological examination, recorded on video
- Psychiatric interview, recorded on video
- Questionnaires (psychiatry, disability and tic assessment)
- CGI severity by examiner based on video neurological examination
- CGI-improvement relative to T = 0 by examiner based on video neurological examination
- Counting the amount of jerks during 10 minutes of the psychiatric interview on video
- UMRS and PMD scores based on the recorded video during neurological examination
- Interview (treatment effective, placebo or BoNT, CGI-S, CGI-I, VAS, adverse events)
- MRC weakness
- fMRI scan (when participating in this sub-study)

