## T = 16 months

- Neurological examination, recorded on video
- Psychiatric interview, recorded on video
- Questionnaires (psychiatry, disability and jerk assessment)
- CGI severity by examiner based on video neurological examination
- CGI-improvement relative to T=0 and T=16 by examiner based on video neurological examination
- Counting the amount of jerks during 10 minutes of the psychiatric interview on video
- UMRS and PMD scale scores based on the recorded video during neurological examination
- Interview (treatment effective, CGI-S, CGI-I, adverse events)
- MRC weakness

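### Adverse events are actively asked about only at week 16 and month 16, so most of the six injection sessions have no scheduled inquiry while side effects would be present

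*Protocol*

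**What the plan says.** The occurrence of adverse reactions is a secondary objective of the randomised trial and an objective of the follow-up study (section 2). Section 7.1.2 makes it endpoint 9 and says how it is measured: "Evaluation of adverse effects via interview and neurological examination".

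The assessment times come from section 3: "Patients will be assessed at baseline, 16 weeks (the trial period) and after 16 months (follow-up study". In 7.3.4 the adverse-event question appears twice. At week 16 it is part of "Interview (treatment effective, placebo or BoNT, CGI-S, CGI-I, VAS, adverse events"), and at month 16 of "Interview (treatment effective, CGI-S, CGI-I, adverse events"). MRC testing for weakness is listed at the same two visits.

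Section 5.1 gives the treatment schedule. The trial phase has "2 times injections with botulinum neurotoxin injections intramuscular with a 3 month interval", or placebo on the same pattern. Then: "After the trial period, all patients will receive 4 injections of BoNT also with 3 month intervals". On the common side effects, section 6.4 states: "These side-effects are reversible and may be expected to resolve within two to four weeks".

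Two other provisions bear on the point. Section 8.2 requires every adverse event that a patient volunteers, or that the investigator or staff notice, to be recorded, with no restriction to particular visits. Section 3 (Intervention) allows the second session to be adjusted in the light of response and any muscle weakness.

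**The concern.** The endpoint is defined by an interview and an examination, but these take place twice, while patients are exposed six times. If common side effects last two to four weeks, an interview many weeks later relies on memory, and an examination at that point cannot find weakness that has already gone. For most sessions the only route left is passive: the patient volunteers the event or someone on the staff notices it. The protocol does not say how passive and solicited reports are to be combined for endpoint 9.

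At stake are the adverse-event rates the trial will report, for the randomised phase and for repeated treatment. In the follow-up part a single interview covers four BoNT sessions and about a year.

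**Working it through.** No stated figure in the protocol depends on this point, and the sample size in 4.4 is unaffected. The check is date arithmetic from each injection session to the next scheduled adverse-event interview.

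**Inputs**
- Interviews: week 16 and month 16 (7.3.4). One month = 365.25 / 12 / 7 = 4.348 weeks, so month 16 = week 69.6.
- Trial sessions: week 0 and week 12. Week 12 follows from 7.1.1: "The primary outcome will be determined 4 weeks after the second injection (t=16 weeks"), and 16 − 4 = 12.
- Follow-up sessions: four, three months apart (5.1). The text does not date the first one, and the time-schedule figure is not available here, so two readings are needed. Reading A continues the three-month spacing (months 6, 9, 12, 15). Reading B starts at week 16 and adds three months each time.

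**Formula:** gap = week of next scheduled interview − week of session. Gaps are computed before rounding.

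| Session | A: week | A: gap (weeks) | B: week | B: gap (weeks) |
|---|---|---|---|---|
| 1 | 0 | 16.0 | 0 | 16.0 |
| 2 | 12 | 4.0 | 12 | 4.0 |
| 3 | 26.1 | 43.5 | 16.0 | 53.6 |
| 4 | 39.1 | 30.4 | 29.0 | 40.5 |
| 5 | 52.2 | 17.4 | 42.1 | 27.5 |
| 6 | 65.2 | 4.3 | 55.1 | 14.4 |

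**Results**
- Reading A: sessions 2 and 6 are followed by an interview at about four weeks, the end of the stated window. The other four wait 16.0 to 43.5 weeks.
- Reading B: only session 2 has an interview at about four weeks. The other five wait 14.4 to 53.6 weeks.
- Randomised phase, both readings: one of two sessions. Side effects of session 1 would be expected to be over 16 − 4 = 12 to 16 − 2 = 14 weeks before the interview.
- Follow-up phase: three of four sessions (A) or four of four (B) have no inquiry near the window.

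**Effect on the comparison.** If the same fraction c of affected patients is identified in each arm, the observed difference is c × (rate on BoNT − rate on placebo). The absolute rates and the absolute difference shrink by the factor c, while the ratio is unchanged. The protocol gives no value for c.

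**Effect of asking at injection sessions only.** The longest wait would fall from 43.5 to about 13.0 weeks under A. Under B it would fall from 53.6 to 14.4 weeks, the gap between the last session and month 16. Both remain well beyond two to four weeks.

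**The case against.** Several points on the other side stand.

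- Section 8.2 captures volunteered and observed events at any time, and it names local pain, flu symptoms, muscle weakness and haematomas for periodic reporting. These are largely the short-lived effects in question. But this is a recording and reporting rule. It does not schedule anyone to ask.
- The session-two adjustment in section 3 implies that weakness after the first injection is looked at about week 12. That covers one type of effect at one session. It is not listed as an outcome assessment, and the injecting neurophysiologist takes no part in outcome assessment.
- Section 7.3.2 speaks of an interview during visits, which could be read to include injection visits. The scheme in 7.3.4 lists it only at week 16 and month 16. The missing time-schedule figure might show further contacts.
- A resolved event can still be remembered, and two to four weeks is an expectation, not a limit.

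A reader might infer more than the protocol supports in four ways:

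- *That the endpoint is undercounted and most events are lost.* This does not follow, because later recall and passive reporting may recover them.
- *That the loss can be put as a percentage, starting from the 28% in section 6.3.* That figure spans a range of other indications and is not tied to two sessions. A recall rate would also have to be invented.
- *That the comparison is biased between arms, because the week-16 interview also asks patients to guess their allocation.* Both arms are blinded and follow one schedule. Nothing in the protocol shows that capture would differ.
- *That the low-risk classification in 8.3 depends on these interviews.* It is a judgement made in advance to explain the absence of a monitoring board.

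**Conclusion.** The point holds as a weakness in the schedule. As written, solicited inquiry and MRC testing follow four or five of the six sessions only after about 14 to 54 weeks, and in the randomised phase this applies to one session of two. The adverse-reaction endpoint may therefore be under-ascertained and dependent on recall. The size of any shortfall cannot be fixed from the protocol. It should be similar in both arms and would mainly lower the absolute rates and the absolute difference.

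This rests on 7.3.4 being the complete list of scheduled inquiries, on one of the two readings of the follow-up dates, and on the protocol's own expectation of how long side effects last. The visit schedule is protocol content, so this is not a detail that an analysis plan would supply.

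**What to change.** In 7.3.4:

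1. Add a brief structured adverse-event inquiry at every injection session, before injection, covering the period since the previous session.
2. Give each patient a one-page event card for the four weeks after each injection. This is needed because asking at sessions alone still leaves gaps of about 13 weeks.
3. State that endpoint 9 is built from the session inquiries, the cards and the two existing interviews, together with the spontaneous and staff-observed reports under 8.2, and say how these sources are combined.

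The cost is a few minutes at sessions patients already attend, one CRF page and the card. Reported event rates are likely to be higher than under the present schedule. Sample size and treatment are unaffected.
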